| AST, ALT, or Increased Bilirubin                         | 2                        | Toxicity resolves to Grade 0-1                                                                                                      | Toxicity does not resolve within 12 weeks of last dose.                                                                                                            |
|                                                          | 3-4                      | Permanently discontinue (see exception below)                                                                           | Permanently discontinue                                                                                                                                            |
| Type 1 diabetes mellitus (if new onset) or Hyperglycemia | T1DM or 3-4              | Hold pembrolizumab for new onset Type 1 diabetes mellitus or Grade 3-4 hyperglycemia associated with evidence of beta cell failure. | Resume pembrolizumab when patients are clinically and metabolically stable.                                                                                        |
| Hypophysitis                                             | 2-3                      | Toxicity resolves to Grade 0-1                                                                                                      | Toxicity does not resolve within 12 weeks of last dose or inability to reduce corticosteroid to 10 mg or less of prednisone or equivalent per day within 12 weeks. |
|                                                          | 4                        | Permanently discontinue                                                                                                             | Permanently discontinue                                                                                                                                            |
| Hyperthyroidism                                          | 3                        | Toxicity resolves to Grade 0-1                                                                                                      | Toxicity does not resolve within 12 weeks of last dose or inability to reduce corticosteroid to 10 mg or less of prednisone or equivalent per day within 12 weeks. |

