**Note: Permanently discontinue for any severe or Grade 3 drug-related AE that recurs or any life-threatening event.**

 For patients with liver metastasis who begin treatment with Grade 2 AST or ALT, if AST or ALT increases by greater than or equal to 50% relative to baseline and lasts for at least 1 week then patients should be discontinued.

 Patients with intolerable or persistent Grade 2 drug-related AE may hold study medication at physician discretion. Permanently discontinue study drug for persistent Grade 2 adverse reactions for which treatment with study drug has been held, that do not recover to Grade 0-1 within 12 weeks of the last dose.

Dosing interruptions are permitted in the case of medical / surgical events or logistical reasons not related to study therapy (e.g., elective surgery, unrelated medical events, patient vacation, and/or holidays). Subjects should be placed back on study therapy within 3 weeks

of the scheduled interruption, unless otherwise discussed with the Sponsor. The reason for interruption should be documented in the patient's study record.

*Note: These evaluations should be done in relation to each pembrolizumab dose. Adverse events that occur or are noted in between scheduled pembrolizumab infusions, but are within 2 weeks after IL-2 administration and appear to meet Table 3 criteria, and have resolved at the point of the next pembrolizumab dose, and are attributed to the IL-2 treatment's acute side effects do not count as events that are required to be managed as indicated in Table 3. For example, grade 3 creatinine elevation that resolved after the IL-2 was finished but before the next pembrolizumab infusion would not count as an AE that requires interruption of the pembrolizumab treatment schedule.*

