### **5.2.2 Timing of Dose Administration**

Trial pembrolizumab treatment should be administered on Day 1 of each 3 week pembrolizumab cycle after all procedures or assessments have been completed as detailed on the Trial Flow Chart (Section 6.0), within the specified window. Trial treatment may be administered up to 3 days before or after the scheduled Day 1 of each cycle due to administrative or other practical reasons.

Pembrolizumab 200 mg target infusion time is to be 30 minutes. However, given the variability of infusion pumps, a window of -5 minutes and +10 minutes is permitted (*i.e.*, infusion time is 30 minutes: -5 min/+10 min, which is 25 to 40 minutes).

The Pharmacy Manual contains specific instructions for the preparation of the pembrolizumab infusion fluid and administration of infusion solution.

*Terminology notes:*

To keep with most of the pembrolizumab development, one “cycle” is designated as a 3 week span of time with one dose of pembrolizumab on the first day. To avoid confusion, for this document, the term “cycle” will be avoided for the IL-2 treatment courses, or for the time in between CT scans.

One “block” for protocol purposes is a group of three (or four) pembrolizumab cycles. The pembrolizumab cycles are numbered a #1, #2, and #3. A fourth cycle will be designated as #4e”, where “e” means extra, for an extra pembrolizumab-only 3-week cycle added to accommodate *any* scheduling issues.

There are eight hospital admissions for IL-2 treatment, which are in the second and third weeks on the first and second cycles of the second and third blocks. These will be designated by the approximate week within the block, using B2 for the second block and B3 for the third block, and thus, for B2: B2W2, B2W3, B2W5, B2W6, and correspondingly for B3W2, B3W3, B3W5 & B3W6.

Since the “week” designation can be affected by intervals that are permissible (such as 6 days, that would technically be during the same (*conventional definition*) calendar week, the protocol document will avoid designating the IL2 doses as being scheduled within a particular “week”, but instead will use the abbreviations defined above. (B2W2, etc.) where possible.

This is the whole schedule:

*Start of block B1:*

Cycle 1 pembrolizumab dose 1. Interval to next dose  $21 \pm 3$  days.

Cycle 2 pembrolizumab dose 2. Interval to next dose  $21 \pm 3$  days.

Cycle 3 pembrolizumab dose 3. Interval to next dose  $21 \pm 3$  days.

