| Prior and Concomitant Medication Review                                                                                               |                         | x                              |                                  |    |    |         |                          |    |    |         |                                      |                                               |                                                |                                        |
| Pembrol Treatment Administration                                                                                                      |                         |                                | x                                | x  | x  |         | x                        | x  | x  |         |                                      |                                               |                                                |                                        |
| IL-2 treatment called "W2" or "W5"                                                                                                    |                         |                                |                                  |    |    |         | x                        | x  |    |         |                                      |                                               |                                                |                                        |
| IL-2 treatment called "W3" or "W6"                                                                                                    |                         |                                |                                  |    |    |         | x                        | x  |    |         |                                      |                                               |                                                |                                        |
| Post-study anticancer therapy status                                                                                                  |                         |                                |                                  |    |    |         |                          |    |    | x       |                                      |                                               |                                                |                                        |

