| PT/INR and aPTT                                                                                                         |                         | x                              |                          |     |     |         |                          |          |     |         |                  |                                             |                                              |                                        |
| CBC with Differential & Comprehensive Serum Chemistry Panel                                                             |                         | x                              |                          |     |     |         | W1
W2                 | W4
W5 | x   |         | x                | x                                           | x                                            |                                        |

| Trial Period:                                                                          | Screening Phase         |                                | Treatment Cycles                      |     |     |         |                          |             |     |         | End of Treatment                | Post-Treatment                           |                                           |                                     |
|----------------------------------------------------------------------------------------|-------------------------|--------------------------------|---------------------------------------|-----|-----|---------|--------------------------|-------------|-----|---------|---------------------------------|------------------------------------------|-------------------------------------------|-------------------------------------|
|                                                                                        |                         |                                | Monotherapy (B1, B4, cE)              |     |     |         | IL2 combination (B2, B3) |             |     |         |                                 |                                          |                                           |                                     |

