† Perform on women of childbearing potential only. If urine pregnancy results cannot be confirmed as negative, a serum pregnancy test will be required.

‡ If considered standard of care in your region.

Laboratory tests timing and evaluation are described in section 6.1 .

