#### **3. Additional adverse events:**

A separate guidance document has been provided entitled “Event of Clinical Interest Guidance Document” (previously entitled, “Event of Clinical Interest and Immune-Related Adverse Event Guidance Document”). This document provides guidance regarding identification, evaluation and management of ECIs and irAEs.

ECIs (both non-serious and serious adverse events) identified in this guidance document from the date of first dose through 90 days following cessation of treatment, or 30 days after the initiation of a new anticancer therapy, whichever is earlier, need to be reported within 24 hours to the Sponsor and within 2 working days to Merck Global Safety. (Attn: Worldwide Product Safety; [contact]), regardless of attribution to study treatment, consistent with standard SAE reporting guidelines.

Subjects should be assessed for possible ECIs prior to each dose. Lab results should be evaluated and subjects should be asked for signs and symptoms suggestive of an immune-related event. Subjects who develop an ECI thought to be immune-related should have additional testing to rule out other etiologic causes. If lab results or symptoms indicate a possible immune-related ECI, then additional testing should be performed to rule out other etiologic causes. If no other cause is found, then it is assumed to be immune-related.

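### The flow chart schedules no blood count or chemistry panel at the pembrolizumab-only doses, contradicting Section 7.3.3.2 and the note to Table 3

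*Combined protocol and SAP*

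**What the plan says.** The flow chart in Section 6.1 has one row for "CBC with Differential & Comprehensive Serum Chemistry Panel". It is marked at main screening; at W1 to W6 and W7 of the IL-2 combination blocks (W3 and W6 stand on the continuation line after the page break); and at discontinuation, safety follow-up and follow-up visits. The four monotherapy columns (w1, w4, w7 and the week-9 evaluation), which cover B1, B4 and extra cycles, are blank. The row "Pembrol Treatment Administration" is marked in three of those four columns.

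The text expects laboratory results at each dose:

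- Section 7.3.3.2, item 3: "Subjects should be assessed for possible ECIs prior to each dose. Lab results should be evaluated". No block is exempted.
- Table 3 (Section 5.2.1.2) acts on grades that come from the chemistry panel, including "AST, ALT, or Increased Bilirubin", hyperglycemia, and renal failure or nephritis. The note beneath it says "These evaluations should be done in relation to each pembrolizumab dose".
- The hepatic event of clinical interest (Section 7.3.3.2, item 2) needs AST or ALT, total bilirubin and alkaline phosphatase taken at the same time.

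On timing, Section 7.2.1 (Laboratory Procedures/Assessments) says "Laboratory tests timing and evaluation are described in section 6.1". Section 5.2.2 (Timing of Dose Administration) has pembrolizumab given once the flow-chart assessments for the visit are complete.

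**The concern.** A site that follows the chart exactly would have no scheduled chemistry at the B1 and B4 dose visits on which to apply Table 3 or the hepatic event definition. Adverse-event tabulation is a co-primary objective (Section 3.2), and Section 4.4.4.1 calls this the first human experience with the two drugs together on this schedule. Section 5.2.1.2 says that immune events may appear several months after dosing.

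B4 matters most. All its patients who received IL-2 belong to the combination treatment population, which feeds both the toxicity boundary in Section 8.5 and the response analysis in Section 8.4. A hepatic or renal event visible only in the laboratory could arise in B4 and be detected late. If it resolved before the discontinuation visit, it might never be recorded. Where testing is left to local habit, capture would also vary between patients.

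**Working it through.** No sample-size or error-rate figure is involved. The check is a reading of the chart and a count of doses and intervals.

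**Column alignment.** After the row label the chart has 14 columns: 2 screening, 4 monotherapy, 4 combination, 1 discontinuation and 3 post-treatment. The CBC/chemistry row and its continuation line each have 14 cells, with 0 of 4 monotherapy cells filled. Nearby rows also have 14 cells and do carry monotherapy marks: pregnancy test at w1, w4 and w7; urinalysis and thyroid tests at w1; pembrolizumab at w1, w4 and w7. A column shift therefore does not explain the blanks.

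**Doses affected.** The plan has 4 blocks × 3 doses = 12 doses. B1 holds doses 1 to 3 and B4 holds doses 10 to 12, so 3 + 3 = 6 doses fall in monotherapy columns. If the screening panel (day −28 to 0) serves dose 1, then 6 − 1 = 5 remain, plus any #4e cycle.

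**Intervals between scheduled panels.** Put dose k on day 21 × (k − 1), the nominal schedule.

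- Screening to B2W1: B2W1 is dose 4, on day 63. From screening on day 0 the interval is 63 days (9 weeks); from day −28 it is 63 + 28 = 91 days (13 weeks).
- B3W7 to the end of B4: B3W7 is dose 9, on day 21 × 8 = 168. B4 ends at 36 × 7 = 252 days. The interval is 252 − 168 = 84 days (12 weeks), and doses 10, 11 and 12 (days 189, 210 and 231) fall inside it.
- One #4e cycle within either interval adds 21 days: 84 to 112 days (12 to 16 weeks) for the first, and 105 days (15 weeks) for the second.

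**Whether other text supplies the missing schedule.** Table 5 lists analytes only. Section 7.2 (Trial Procedures) allows unscheduled testing when the investigator judges it clinically necessary, which is discretionary. The IL-2 checklist in Section 5.2.4 applies before IL-2 doses, and none are given in B1 or B4. The hepatic guidance in Section 5.7.1 asks for more frequent liver tests after a Grade 2 event, which presupposes that the event has been found. None of these puts a panel at a named B1 or B4 visit.

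**The case against.** The strongest reply is that a site must follow the whole protocol. Section 7.3.3.2 already calls for laboratory results around each dose, so the chart merely fails to list what the text expects. That is fair, and it rules out reading the protocol as a plan to dose without laboratory results. It does not remove the contradiction, because Section 7.2.1 (Laboratory Procedures/Assessments) refers timing to the chart and Section 5.2.2 defines pre-dose work by it.

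A second reply is that the row breaks across a page and a mark may have been lost when the PDF was read. This cannot be excluded outright, and the chart has other oddities: tumor imaging is marked at monotherapy w1 rather than the week-9 evaluation, although Section 5.3 places it at the end of each block. The intact cell counts make a loss unlikely, and the sponsor can check the source chart at once.

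Several stronger readings are tempting but not supported:

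- *Patients start IL-2 without interim chemistry.* The panel is marked at B2 W1 and W2. The Section 5.2.4 checklist sets a creatinine condition for starting a course and has electrolytes and liver tests reviewed.
- *B4 follows the last IL-2 with no laboratory check between.* The last IL-2 admission is B3W6; B3W7, with its marked panel, comes next.
- *Toxicity-boundary events in B1 would be lost.* This is weak. The boundary counts the combination treatment population, and the recording period in Table 6a of Section 7.3.4 begins after the first IL-2 dose.
- *No laboratory work at all is scheduled in these blocks.* Urinalysis and thyroid tests are marked at monotherapy w1; the gap is specific to blood count and chemistry.

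**Conclusion.** The contradiction stands. The chart schedules no blood count or chemistry panel at the pembrolizumab-only doses, while Section 7.3.3.2 and the note to Table 3 tie laboratory-based evaluations to each dose. Its size is five of 12 planned doses plus any #4e cycle, assuming that the screening panel serves the first dose; without that assumption it is six. The 13-week figure is a maximum that applies when screening falls on day −28. All intervals assume nominal 21-day spacing.

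The gap is the run of doses within B1 and within B4, not the start or end of IL-2. The consequence is possible late or missed detection of laboratory-only events, above all in B4, for Table 3, for reporting of events of clinical interest and for the co-primary adverse-event tabulation. The response-rate endpoint and its two-stage decision rule are not affected. Because the conflict concerns safety rules and is cheap to remove, it should be corrected rather than left to local practice.

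**What to change.** By amendment, the sponsor should reconcile the CBC/chemistry row of the Section 6.1 chart with Table 3 and its note (Section 5.2.1.2) and with items 2 and 3 of Section 7.3.3.2. Chart and text should then agree on which pembrolizumab-only doses have laboratory results available, including any #4e cycle, and on whether the screening panel counts for the first dose. Which passage governs is the sponsor's decision; this point proposes no monitoring schedule.

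The cost is one amended row or matching text edits. If the text governs, it also means routine local blood draws at infusion visits that already take place; blood is already taken at monotherapy w1 for thyroid tests. No new visit or invasive procedure is needed.

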### 3.4 Exploratory Objectives

These objectives are expected to be developed as part of testing in parallel with testing of patients on other trials. While the specific conceptual goals are outlined here, the specific tests are not prespecified.

(1) **Objective:** Exploratory analyses dividing retrospectively designated best responders versus remaining patients with respect to a variety of cell subsets, for example: DC:MDSC ratio; CD4+ : CD4: FoxP3+ ratio. CD8+ : NK cell ratio.

**Hypothesis:** Pretreatment leukocyte characteristics will predict response

(2) **Objective:** Exploratory analyses dividing retrospectively designated best responders versus remaining patients with respect to sets of immune related proteins assayed by Nanostring™ testing of tumor specimens for gene sets that have been proposed to be related to the chance of anticancer immune response.

**Hypothesis:** The good-responder patients will have an overall pattern consistent with those seen patients with other diagnoses who had had good response after other PD-1 treatment. For example, better responses if there is tissue PD-L1 expression > 5%, or interferon-gamma related gene expression.

(3) **Objective:** Exploratory analyses of selected serum proteins to analyze for markers of immune response.

**Hypothesis:** The good-responder patients will have an overall pattern consistent with those seen patients with other diagnoses who had had good response after other PD-1 treatment.

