| Correlative Studies Blood Collection**
(30 ml per time point)                       |                         | Pre-treatment (or B1W1)        | B4
W1                              |     |     |         | Pre B2
W2             | At B2
W4 |     |         |                                 |                                          |                                           |                                     |

\* B1W1 = this is by definition the first treatment day, so +/- 3 does not apply. B4: the +/-3 does apply.

\*\* Correlative blood specimen collection procedure:

Vaccutainer type or CPT tubes will be used for collection of 30 ml peripheral blood specimens. The tubes should be filled and inverted 8-10 times after collection and prior to separation. The samples should be processed within 8 hours of collection and should not be refrigerated or frozen.

Peripheral blood mononuclear cells (PBMC) will be isolated by density centrifugation using Ficoll™ and the cells will be frozen in 10% DMSO, 90% fetal calf serum and stored in vapor phase liquid nitrogen until ready for testing.

Serum will be isolated by centrifugation and frozen similarly.

Specimens will be stored in the Tissue Core repository.

The PI will designate which specimens will be analyzed, based on factors including disease response and dose delivery.

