## 8.1 STATISTICAL ANALYSIS PLAN

### 8.2 Statistical Analysis Plan Summary

Overall response rate (ORR) and the 95% confidence interval of that estimate will be obtained through binomial distribution theory, using the ITT population, with a one-sided endpoint, for the primary endpoint. Progression free survival, overall survival, landmark one-year progression free survival, landmark one-year overall survival will be obtained by Kaplan-Meier method.

The adverse events will be tabulated descriptively, by grade. All AEs will be summarized by system organ class and preferred term. Listings and summary tables will be provided. Separate data listings and summaries will be presented for all serious adverse events (SAEs) and deaths.

The correlative study tests will be analyzed as an exploratory assessment, or as part of a separate correlative protocol.

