## 8.6 Correlative studies on specimens of tumor and of blood specimens:

These are all secondary endpoints,

Responders versus remaining patients will be compared.

The following tissue markers will be considered for correlative testing.

- (1) Quantitation of circulating cells with flow cytometry counts for cells with lymphocyte phenotypes of CD3+, CD4+, T-regulatory, CD8+, NK+, MDSC, or DC, and conventional

differential for granulocytes, platelets or other subtypes. The relevant ratios, such as DC: MDSC ratio; CD4+ : CD4/FoxP3+ ratio; CD8+ : NK cell ratio will be computed.

- (2) On the pretreatment tumor specimen, quantitation of infiltrating leukocytes that are positive for CD3, CD4 or CD8, by immunohistochemistry.
- (3) On the pretreatment tumor specimen, quantitation of PD-L1.
- (4) Quantitation of serum cytokines including but not limited to: CXCL9, CXCL10

[figure not shown]
If the data follow a normal distribution, t test will be used for biomarker level comparison. If the data do not follow normal distribution then a power transformation (e.g. square-root, log) or non-parametric Wilcoxon rank-sum test approach will be adopted. The Bonferroni-Holm approach will be used to account for multiple testing to control type I error at 5%. Some tests may be dropped from the multiple testing group prior to analysis after the overall distribution of the biomarker is examined, but before it is divided by response group. Tests outside the multiple testing group will be studied at alpha = .05 individually, and considered as exploratory analyses.

- (5) CD8+ lymphocyte subset analyses of gene expression; using the NanoString product, Multiplexed Cancer Immune Response Analysis nCounter® PanCancer Immune Profiling Panel for Gene Expression. A similar assay on other leukocyte subsets may be performed.

The 760 genes expressed will be compared for the responders versus the nonresponders, for the baseline specimens.

The 760 genes expressed will be compared for the specimens after the 3 on treatment specimens versus baseline specimens.

These analyses will identify genes for which there is a statistically significant difference of expression level. The description of these genes' expression difference will be the endpoint, to address the hypothesis that differences of CD8+ gene expression are a consequence of the treatment with these medications that have targets on lymphocytes.

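### Discretionary choice of specimens for assay, using response and dose delivery, can bias the responder comparison, and the Holm adjustment does not correct for it

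*Combined protocol and SAP*

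**What the plan says.** Specimens are stored, and the footnote to the flow chart in Section 6.0 states how they are chosen for assay: "The PI will designate which specimens will be analyzed, based on factors including disease response and dose delivery". The list of factors is open-ended. Section 5.2.3 confirms that the trial is open-label.

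Section 8.6 sets out what is done with the results. For the markers, "Responders versus remaining patients will be compared". For gene expression, "The 760 genes expressed will be compared for the responders versus the nonresponders, for the baseline specimens", and also "The 760 genes expressed will be compared for the specimens after the 3 on treatment specimens versus baseline specimens". On error control for the markers, "The Bonferroni-Holm approach will be used to account for multiple testing to control type I error at 5" percent. Tests may be dropped from that family, but only "after the overall distribution of the biomarker is examined, but before it is divided by response group".

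The labels differ. Section 3.4 describes "Exploratory analyses dividing retrospectively designated best responders versus remaining patients" and leaves the individual tests open. Section 8.2 says: "The correlative study tests will be analyzed as an exploratory assessment, or as part of a separate correlative protocol". Section 8.6 calls the same work secondary.

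No section gives a minimum number of specimens to assay, a random draw, weighting, or laboratory blinding to response.

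**The concern.** Response helps decide who is assayed, and the results are then compared by response. Dose delivery, a post-baseline variable, is a second selection factor and may be linked to response. Under Section 5.9, confirmed progression ends treatment, with exceptions, so non-responders will tend to receive fewer doses. Under the Subject Replacement Strategy, a patient with an apparent complete response after block 1 may receive no IL-2. A choice that uses dose delivery can therefore fall unevenly on the two groups.

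Section 3.4 hypothesizes that pretreatment leukocyte features predict response. If the assayed non-responders are an unrepresentative subset of all non-responders, a marker with no relation to response can appear to predict it. The plan guards against choosing tests after seeing results by response, but has no matching guard on choosing specimens. Holm adjustment deals with the number of tests. It assumes that each p-value is valid to begin with.

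**Working it through.** **1. Cohort available.** The documents give no figure for the correlative comparison itself, so the starting point is the Simon design in Section 8.4 (15 patients, stop at 3 or fewer responses; 24 in all, reject at 7 or fewer; response rates 0.20 and 0.45).

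- Early termination at 0.20: the sum over x = 0 to 3 of C(15,x) × 0.2^x × 0.8^(15−x) = 0.648 (plan: 0.65).
- Expected size: 15 + (1 − 0.648) × 9 = 18.17 (plan: 18).
- Exact type I error 0.0835 (plan limit 10%) and power 0.900 (plan: 90%).

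The plan's figures reproduce. With all 24 assayed, the expected groups are 24 × 0.20 = 4.8 responders against 19.2 at a 20% response rate, and 24 × 0.45 = 10.8 against 13.2 at 45%.

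**2. Effect of selection on a marker unrelated to response.** Simulation of 24 patients, 6,000 runs per scenario, two-sided t test at 0.05, response rate 20% or 45%. Runs with fewer than two specimens in either group were dropped. The marker and dose delivery are standard normal with correlation ρ. The documents give no ρ, so 0 to 0.7 is an assumed range.

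| Specimens assayed | ρ | False positives | Mean spurious difference (SD) |
|---|---|---|---|
| All | any | 5.0% to 5.3% | about 0 |
| All responders, equal number of random non-responders | any | 4.7% to 5.4% | about 0 |
| Same dose-delivery cut for everyone | 0 to 0.7 | 4.6% to 5.6% | about 0 |
| All responders, half of non-responders with highest dose delivery | 0 | 4.8% to 5.2% | about 0 |
| Same | 0.3 | 7.3% | −0.23 to −0.24 |
| Same | 0.5 | 11% to 12% | −0.39 |
| Same | 0.7 | 18% | −0.54 to −0.55 |

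The Monte Carlo standard error near 5% is about √(0.05 × 0.95 / 6000) = 0.28 percentage points, slightly more where runs were dropped. The first three rows are therefore compatible with 5%.

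**3. Check by formula.** Keeping the upper half of a normal variable moves its mean by √(2/π) = 0.80 SD in large samples. The kept non-responders' marker mean then moves by 0.80ρ, which is 0.24, 0.40 and 0.56 at the three correlations, close to the simulated sizes. By symmetry, keeping the lower half would reverse the sign.

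**4. Pooled on-treatment versus baseline comparison.** Let p be the response rate and D the responder minus non-responder difference in mean change. The full-cohort mean change weights responders by p. A half-and-half sample weights them by 0.5. The shift is (0.5 − p) × D, which is 0.30 D at p = 0.20 and 0.05 D at p = 0.45. Selection on response alone, harmless in step 2, therefore distorts an unweighted pooled estimate.

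**The case against.** A reader might infer that selecting on response and then comparing by response is biased in itself. It is not. The second row of the table shows no inflation, and the recommended random draw is itself stratified by response. A reader might also picture the investigator picking extreme responders and poorly dosed non-responders. The footnote says nothing of the kind, and because specimens are frozen until testing, their assay results would not normally be known when they are chosen.

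Dose delivery can also have a legitimate role. Figure 4 in Section 4.4.4.2 defines the on-treatment specimens by the doses that precede them, and a specimen taken without those doses does not represent its time point. A single exposure criterion for everyone produced no bias in the simulation.

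Finally, Sections 3.4 and 8.2 call this work exploratory, which limits what would be claimed from it.

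The first three arguments stand, and they narrow the point to unspecified choice within response groups. The exploratory label stands only in part, because Section 8.6 calls these endpoints secondary and sets a 5% error rate for the markers. Nothing in the footnote confines dose delivery to the uses that are harmless.

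**Conclusion.** The point holds as a possibility that the plan leaves open. Bias in the responder comparison needs two conditions: selection within the groups that differs by response, and a link between what drives that selection and the marker. The footnote permits the first; whether the second applies is unknown. The inflation to between 7.3% and 18% illustrates one selection pattern under assumed correlations and is not an estimate for this trial. Neither size nor direction can be derived from the documents.

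The consequences stop at the correlative work. A reader might worry that the efficacy conclusion is affected too, but the primary response rate, the Simon decision and the toxicity boundary do not use these assays. The sentence should be changed because it undermines an error rate that the plan states and the change costs little.

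**What to change.** Replace the footnote sentence with a rule, and repeat it in Section 8.6:

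- Assay all usable specimens at each planned time point, baseline and the three on-treatment points. If budget limits the number, the biostatistician draws patients at random within responders and within non-responders, with no choice by the investigator. The responder definition has to be fixed before the draw; confirmed CR or PR, as in Section 8.4, would serve.
- Do not use dose delivery to select baseline specimens. Any exposure requirement for an on-treatment specimen, for example that the doses defining its time point were given, is fixed in advance and applied identically to both groups.
- Blind the laboratory to response.
- If sampling fractions differ by response, weight pooled estimates such as on-treatment versus baseline change.
- Report specimens available and specimens assayed, by response group.

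The cost is the loss of investigator discretion, a short text change and a little more analysis work. Assaying everything may need more assays than a selected subset; the random draw does not. Treatment and the primary analysis are unchanged.
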